5.3. Study Population

5.3.1 Selection Criteria

Patient selection criteria for the U-500R Syringe Initiators [Index Event 1a]:

- Include patients who had ≥ 1 prescription claim for U-500R vial during the identification period (VHA and LCED: 01JAN2014-30JUN2017; Truven: 01APR2014-30SEP2017)—the first prescription claim for U-500R vial will be designated as index Event 1a (U-500R syringe initiation), and the date will be designated as the index date;
- Include patients who had ≥ 2 claims with an ICD-9/10-CM code (Appendix 1) for T2DM in any position (primary/secondary) at any time prior to the index date;
- Exclude patients who had both T1DM and T2DM, had no oral anti-diabetic drug (OADs; Appendix 1) other than metformin, and the ratio between the number of T1DM and T2DM claims > 0.5 at any time in the study period (VHA and LCED: 01APR2013-31MAR2018; Truven: 01JUL2013-30JUN2018);
- Include patients who were aged ≥ 18 years on the index date;
- Include patients who had continuous health plan enrollment with medical and pharmacy benefits for ≥ 9 months pre- and post-index event;
- Exclude patients with no evidence of insulin including U-500R (any type; Table 2) in the 9 months pre-index period (baseline);

[2018-7241 Study Identifier] Observational Study Protocol

- Exclude patients with ≥ 1 prescription claim for U-500R use in the 9 months pre-index period;
- Include patients who had ≥ 1 prescription claim for any insulin other than U-500R in the 9-month pre-index period;
- Include patients who had ≥ 1 HbA1c measurement within 90-day pre-index or 30-day post-index event;
- Include patients who had ≥ 1 HbA1c measurement after the 30-day post-index period at any time in the 9-months follow-up period;
 - Patients with ≥ 1 HbA1c measurement after the 30-day post-index and within 30 days prior to the end of the 9-months follow-up period will be flagged; and
 - Patients with ≥ 1 HbA1c measurement after the 30-day post-index and within 2 months prior to the end of the 9-months follow-up period will be flagged;
- Exclude patients who had ≥ 1 claim with a ICD-9/10-CM code (Appendix 1) for secondary diabetes, gestational diabetes, diabetes complicating pregnancy, childbirth, or puerperium, or non-clinical diabetes at any time during the 9-month baseline period;
- Exclude patients who had claims indicating pump use (Appendix 2) in the 9-month post-index (follow-up) period;

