- Exclude patients who had claims indicating TDD above 2000 units/day at any time in the pre-index or post-index periods.

Sample selection criteria for U-500R Kwikpen Initiators [Index Event 1b]

- Include patients who had ≥ 1 prescription claim for U-500R Kwikpen administration during the identification period (VHA and LCED: 01JAN2014-30JUN2017; Truven: 01APR2014-30SEP2017)–the first prescription claim for U-500R Kwikpen administration will be designated as Index Event 1b, and the date will be designated as the index date;
- Include patients who had ≥ 2 claim with an ICD-9/10-CM code (Appendix 1) for T2DM in any position (primary/secondary) at any time prior to the index date;
- Exclude patients who had both T1DM and T2DM, had no OADs (Appendix 1) other than metformin, and the ratio between the number of T1DM and T2DM claims >0.5 at any time in the study period (VHA and LCED: 01APR2013-31MAR2018; Truven: 01JUL2013-30JUN2018);
- Include patients who were aged ≥ 18 years on the index date;
- Include patients who had continuous health plan enrollment with medical and pharmacy benefits for ≥ 9 months pre- and post-index event;

[2018-7241 Study Identifier] Observational Study Protocol

- Exclude patients with no evidence of insulin including U-500R (any type; Table 2) in the 9 months pre-index period (baseline);
- Exclude patients with ≥ 1 prescription claim for U-500 use in the 9 months pre-index period;
- Include patients who had ≥ 1 prescription claim for any insulin other than U-500R (Table 2) in the 9-month pre-index period;
- Include patients who had ≥ 1 HbA1c measurement within 90-day pre-index or 30-day post-index event;
- Include patients who had ≥ 1 HbA1c measurement after the 30-day post-index period at any time in the 9-months follow-up period;
 - Patients with ≥ 1 HbA1c measurement after the 30-day post-index and within 30 days prior to the end of the 9-months follow-up period will be flagged; and
 - Patients with ≥ 1 HbA1c measurement after the 30-day post-index and within 2 months prior to the end of the 9-months follow-up period will be flagged;
- Exclude patients who had ≥ 1 claim with a ICD-9/10-CM code (Appendix 1) for secondary diabetes, gestational diabetes, diabetes complicating pregnancy, childbirth, or puerperium, or non-clinical diabetes at any time during the 9-month baseline period;
- Exclude patients who had evidence of pump use (Appendix 2) in the 9-month follow-up period;

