- Exclude patients who had claims indicating TDD above 2000 units/day at any time in the pre-index or post-index periods.

Sample Selection Criteria for U-500R Device Switchers from Syringe to Kwikpen [Index Event 2]

- Include patients who had ≥ 1 claim for U-500R Kwikpen administration in the identification period (VHA and LCED: 01JAN2014-30JUN2017; Truven: 01APR2014-30SEP2017)–the first prescription claim for U-500R Kwikpen administration will be designated as the Index Event 2, and the date will be designated as the index date;
- Include patients who had ≥ 2 claim with an ICD-9/10-CM code (Appendix 1) for T2DM in any position (primary/secondary) at any time prior to the index date;
- Exclude patients who had both T1DM and T2DM, had no OADs (Appendix 1) other than metformin, and the ratio between the number of T1DM and T2DM claims > 0.5 at any time in the study period (VHA and LCED: 01APR2013-31MAR2018; Truven: 01JUL2013-30JUN2018);
- Include patients who were aged ≥ 18 years on the index date;
- Include patients who had continuous health plan enrollment with medical and pharmacy benefits for ≥ 9 months pre- and post-index event;
- Include patients who had ≥ 1 prescription claim for U-500R vial use in the 9-month baseline period;

[2018-7241 Study Identifier] Observational Study Protocol

- Include patients who had ≥ 1 HbA1c measurement within 90-day pre-index event or 30-day post-index event; and
- Include patients who had ≥ 1 HbA1c measurement after the 30-day post-index period;
 - Patients with ≥ 1 HbA1c measurement after the 30-day post-index and within 30 days prior to the end of the 9-months follow-up period will be flagged; and
 - Patients with ≥ 1 HbA1c measurement after the 30-day post-index and within 2 months prior to the end of the 9-months follow-up period will be flagged;
- Exclude patients who had ≥ 1 claim for U-500R Kwikpen administration in the 9-month baseline period;
- Exclude patients who had ≥ 1 claim with a ICD-9/10-CM code (Appendix 1) for secondary diabetes, gestational diabetes, diabetes complicating pregnancy, childbirth, or puerperium, or non-clinical diabetes at any time during the 9-month baseline period;
- Exclude patients who had claims indicating pump use (Appendix 2) in the identification period;
- Exclude patients who had claims indicating TDD exceeding 2000 units/day at any time in the pre-index or post-index periods.

Note:

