5.3.2 Subject Groups

After applying the inclusion and exclusion criteria, our analysis will focus on the following cohorts.

Index Event 1a

- U-500R Syringe Initiators Cohort: Patients who initiated U-500R syringe administration (index event 1a) on their index date.

Index Event 1b

- U-500R Kwikpen Initiators Cohort: Patients who initiated U-500R Kwikpen administration (index event 1b) on their index date.

Index Event 2

- U-500R Device Switchers Cohort: Patients who switched from U-500R syringe to Kwikpen will be included in this cohort.

Note: U-500R syringe/ Kwikpen initiators cohorts who were identified based on the index event 1a or 1b were U-500R naïve patients who did not have any evidence of U-500R use prior to the index date; whereas patients in U-500R device switchers cohort identified from index event 2 had been exposed to U-500R prior to the index date due to U-500R syringe use.

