5.4 Time Periods

The study period will range from 01APR2013-31MAR2018 for VHA and LCED; and 01JUL2013-30JUN2018 for Truven MarketScan claims. The identification period will be 01JAN2014-30JUN2017 for VHA and LCED; and 01APR2014-30SEP2017 for Truven MarketScan claims; the baseline and follow-up periods will be 9 months pre- and 9 months post-index date, respectively (Figures 1-3).

[2018-7241 Study Identifier] Observational Study Protocol**5.5 Variables/Measures**

Table 3 presents the study variables and operational definitions.

Table 3 Variables and Definitions

Variable	Source	Definition
Exposure		
Insulin use	Truven: Outpatient pharmacy claims table VHA: Pharmacy file	Index Event 1a : any insulin use other than U-500R in the pre-index and U-500R syringe use in the post-index period; Index Event 1b : any insulin use other than U-500R in the pre-index and U-500R Kwikpen use in the post-index period; and Index Event 2 : U-500R syringe use in the pre-index and U-500R Kwikpen use in the post-index period.
Baseline Characteristics*		
Age	Truven: Inpatient service table, outpatient service table, outpatient pharmacy claims table VHA: Enrollment file	Age will be retained in the dataset as a continuous variable for groups aged 18-25, 26-35, 36-45, 46-55, 56-64, and ≥ 65 years.
Sex	Truven: Inpatient service table, outpatient service table, outpatient pharmacy claims table VHA: Enrollment file	A flag will be created for male and female patients.
Race (only VHA)	VHA: Enrollment file	A flag will be created for White, Black, and other race patients.
U.S Region (only Truven)	Truven: Inpatient service table, outpatient service table, outpatient pharmacy claims table	A flag will be created for patients belonging to Northeast, Northcentral, South and West regions
Medicare eligibility (Only Truven)	From Truven	A flag will be created for patients who are enrolled in Truven Medicare
Body mass index (BMI)	VHA: Vital Status file	BMI on the index date will be calculated and reported as a continuous variable.
Quan-Charlson comorbidity index (CCI) Score ¹⁶	Truven: Inpatient service table, outpatient service table VHA: Inpatient and outpatient files	Quan-CCI score will be constructed using enhanced ICD-9/10-CM codes for 17 different comorbid conditions.

[2018-7241 Study Identifier] Observational Study Protocol

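### Device switchers are screened for pump use over a fixed calendar window that can miss their follow-up, and the U-500R-naïve label on initiators goes further than the 9-month check behind it

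*Protocol*

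**What the plan says.** **Pump use (Protocol 5.3.1).** The three cohorts do not share one rule.

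- Syringe initiators: "Exclude patients who had claims indicating pump use (Appendix 2) in the 9-month post-index (follow-up) period".
- Kwikpen initiators: "Exclude patients who had evidence of pump use (Appendix 2) in the 9-month follow-up period".
- Device switchers: "Exclude patients who had claims indicating pump use (Appendix 2) in the identification period".

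Section 5.4 makes the last of these a calendar window, the same for every patient: "The identification period will be 01JAN2014-30JUN2017 for VHA and LCED; and 01APR2014-30SEP2017 for Truven MarketScan claims". Follow-up belongs to the patient: "the baseline and follow-up periods will be 9 months pre- and 9 months post-index date, respectively". No reason is given for treating switchers differently.

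**Naïve status.** The note in section 5.3.2 says the initiators "were U-500R naïve patients who did not have any evidence of U-500R use prior to the index date", with no time limit. The criterion for Kwikpen initiators is "Exclude patients with ≥ 1 prescription claim for U-500 use in the 9 months pre-index period", and syringe initiators have the matching 9-month criterion. The index date is the date of the earliest prescription fill for the device in question (vial for 1a, Kwikpen for 1b) in the identification period.

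**The concern.** A pump exclusion should describe the months in which a patient's exposure and outcomes are measured. The switchers' rule does not, and it errs in both directions. Pump use after the identification period closes goes unseen even though follow-up is still running. A pump claim years before the switch, or after follow-up has ended, can remove a patient who had none in the 18 months under study.

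This matters because section 3 says that off-label pump delivery of U-500R is increasing. Under Table 3, switchers' post-index adherence counts Kwikpen claims only, and a gap of more than 60 days after run-out is a discontinuation. A switcher who moves to a pump in unscreened follow-up would show low Kwikpen PDC or a discontinuation. That patient's follow-up HbA1c and hypoglycemia would reflect pump delivery while being attributed to the Kwikpen.

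For initiators, the before-and-after contrast is presented as first exposure to U-500R. If some Kwikpen initiators used vials earlier, the cohort is not the one section 5.3.2 describes.

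**Working it through.** The protocol gives no figure for either gap, so the check is calendar arithmetic on its stated windows.

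**1. Do the windows fit together?** The study period is given as "The study period will range from 01APR2013-31MAR2018 for VHA and LCED; and 01JUL2013-30JUN2018 for Truven MarketScan claims". Identification start minus 9 months is 01APR2013 (VHA, LCED) and 01JUL2013 (Truven). Identification end plus 9 months is 30MAR2018 and 30JUN2018. Both agree with the study period to within a day, so follow-up is meant to run up to 9 months past the identification period.

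**2. Unscreened follow-up for switchers.** The identification period is 42 months. For an index date *t* months into it, unscreened follow-up = max(0, *t* + 9 − 42) months, which is positive when *t* > 33. A VHA switch on 30JUN2017 has essentially all 9 months unscreened.

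The protocol gives no distribution of switch dates. Assume they are even over the last *m* months of identification. Then the share of switchers affected is 9/*m*. Those affected lose 4.5 of 9 months on average, so the share of follow-up time lost is half of 9/*m*.

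| *m* (months) | Switchers with some unscreened follow-up | Follow-up time unscreened |
|---|---|---|
| 42 | 9/42 = 21.4% | 10.7% |
| 24 | 9/24 = 37.5% | 18.8% |
| 18 | 9/18 = 50.0% | 25.0% |
| 12 | 9/12 = 75.0% | 37.5% |

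A day-by-day count on the VHA/LCED dates gives 21.3%, 37.2%, 49.7% and 74.5% for the middle column, and 10.7%, 18.7%, 24.9% and 37.4% for the last. Section 5.1 calls the Kwikpen recently available but gives no launch date. That points towards the lower rows without fixing one.

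**3. Exclusions in the other direction.** A VHA patient who switches in mid-2017 is removed by a pump claim in early 2014, long before baseline. A patient who switches on 01JAN2016 ends follow-up around 01OCT2016, yet is removed by a pump claim in early 2017.

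**4. What the calendar window does cover.** It contains the whole 9-month baseline for any VHA/LCED switcher indexed from about 01OCT2014. That is 42 − 9 = 33 of 42 months, or 79% if dates are even.

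**5. Look-back for naïve status.** From 01APR2013 to 30JUN2017 is 51 months, so at the last index date the criterion checks 9/51 = 18% of the database window. Averaged over index dates, the window before index is about 30 months, and 9/30 = 30% is checked. Two cases then differ:

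- *Same device.* A patient with vial claims in 2014 and again in 2016 is indexed in 2014, because index is the first vial claim in identification. What escapes is a claim in the 9 months before identification opens (up to about 275 days) that also lies more than 9 months before index.
- *Other device.* The first-claim rule looks only at its own device. A patient who used vials in 2014, stopped, and first filled a Kwikpen in 2016 passes the 9-month check. With another insulin in baseline, and the remaining criteria met, that patient enters as a naïve Kwikpen initiator. The patient cannot be a switcher, because switchers need a vial claim in the 9-month baseline.

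**The case against.** Four objections have weight.

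- **Direction of the harm.** A reader might infer that pump-delivered insulin inflates switchers' post-index TDD or PDC. Table 3 and the note under it do not support this: only Kwikpen claims count after the switch, so vial insulin run through a pump enters neither. A patient who leaves the Kwikpen has also truly stopped the index medication as Table 3 defines it. What remains is that a change of delivery method is recorded as poor adherence or discontinuation, and that HbA1c and hypoglycemia are misattributed. Nor are the initiator cohorts free of pump gaps, since neither is screened for pump use in baseline.
- **The obvious repair.** Copying the initiators' follow-up-only rule looks natural, but it would drop the baseline screening that the calendar window now gives most switchers. Their baseline vial claims are read as syringe use, so an unnoticed pump there is a direct misclassification. This objection stands and shapes the fix.
- **Size.** The shares above measure exposure to a gap, not patients with pump claims. The protocol gives no pump-claim rate, and the effect is probably modest if such claims are rare. This also stands.
- **Naïve status.** A fixed washout matched to the required enrollment is ordinary new-user design. Enrollment is guaranteed for only 9 months before index, so the 51 months are a database window, not observed patient time. A reader might infer that the washout is invalid, or that all U-500R use before 9 months is missed. Neither follows, because the first-claim rule catches most earlier use of the same device. The fault is the unqualified sentence in section 5.3.2 together with the gap for the other device.

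**Conclusion.** Both points hold, with different weight.

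The pump window is the stronger. Eligibility of switchers depends on calendar date, differs from the other cohorts without a stated reason, and leaves follow-up unscreened for 21% of switchers under even index dates over 42 months. With index dates in the last 18 to 12 months the figure is 50–75%. The matching shares of follow-up time are about 11% and 25–37%. All of these rest on the assumed spread of index dates. How many patients have a pump claim in the gap, and how far results would move, cannot be derived from the protocol.

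The naïve point is a mismatch between a description and the criteria meant to deliver it. Its clearest case is the former vial user returning on a Kwikpen after more than 9 months. The protocol gives no basis for saying how much this dilutes the initiation contrast, and it does not show that a longer washout is required.

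**What to change.** **Pump use.** In the Index Event 2 criteria of section 5.3.1, replace the identification period with a window tied to the index date that covers both the 9-month baseline and the 9-month follow-up.

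**Naïve status.** In the note to section 5.3.2, state that initiators had no U-500R claim in the 9 months before index. Add a sensitivity analysis that excludes initiators with any earlier U-500R claim, vial or pen, in the available data. Note there that look-back beyond 9 months varies with index date and enrollment.

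**Cost.** Two lines of wording, a rerun of the selection code and one added sensitivity analysis. No new data are needed, because the study period already contains every window. The change in cohort size is likely to be small, but it cannot be computed from the protocol.

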5.1 Summary of Research Design

This will be a retrospective cohort study using the Veterans Health Administration (VHA) database, linked Truven MarketScan Claims and Electronic Medical Records [EMR] Data (LCED), as well as the Truven MarketScan claims databases (Table 1).

Multiple datasets will be used due to unavailability of the certain study outcomes in one single dataset. (e.g. out-of-pocket costs are not available in VHA dataset; HbA1c not available in Truven claims dataset). Additionally, using multiple datasets will improve the generalizability of the study, and since U-500R Kwikpen is recently available in the market, linking two databases would ensure that the study has adequate sample size. Furthermore, the patient population in the VHA primarily consists of veterans across the country (non-commercial database), whereas Truven is an employment-based health insurance (commercial database). Therefore, conducting the analysis separately in each of these databases as well as in the pooled dataset would give a more comprehensive and complete picture of the treatment patterns and outcomes in the real-world in this patient population.

To meet the analytical requirement of multiple research objectives, the following criteria will be used:

- The first prescription claim date for U-500R syringe or U-500R Kwikpen administration will be considered U-500R initiation and designated as Index Event 1 (syringe: Index Event 1a; Kwikpen: Index Event 1b).
- The date for U-500R device switch from syringe to Kwikpen will be designated as Index Event 2.
- The study period will range from 01APR2013-31MAR2018 for VHA and LCED; and 01JUL2013-30JUN2018 for Truven MarketScan claims.
- The identification period will be 01JAN2014-30JUN2017 for VHA and LCED; and 01APR2014-30SEP2017 for Truven MarketScan claims; the baseline and follow-up periods will be 9 months pre- and 9 months post-index date, respectively (Figures 1-3).

[2018-7241 Study Identifier] Observational Study Protocol**Table 1 Study Design by Objectives**

Research Objectives	Database (study period)	Study Cohorts
Research Objective 1		
Primary Objective 1	
 • VHA (01APR2013-31MAR2018) • Pooled VHA and LCED (01APR2013-31MAR2018) • Truven MarketScan Claims Database (01JUL2013-30JUN2018) 	U-500R syringe initiators U-500R Kwikpen initiators U-500R device switchers
Research Objective 2		

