- Since the Truven claims database does not have the lab data, the criteria to have at least 1 HbA1c will be removed from the inclusion criteria while using this database.
- The corresponding ICD-9/10 codes for all the diagnoses and the NDC codes for the insulins are provided in Appendix 1.

Table 2. Classification of Insulin Products

Insulin Class	Generic Name	Product Name
Inhaled Insulin	Insulin Human Inhaled	AFREZZA
		EXUBERA
		EXUBERA COMBINATION PACK 12
		EXUBERA COMBINATION PACK 15
		EXUBERA KIT
Intermediate-Acting Insulin	Insulin Human Zinc (lente)	HUMULIN L
	Insulin Human Isophane (nph)	HUMULIN N (NPH)
		HUMULIN N (NPH) KWIKPEN
		HUMULIN N PEN
		INSULATARD HUMAN INSULIN
		MIXTARD HUMAN INSULIN 70/30
		NOVOLIN N
		NOVOLIN N (NPH)

[2018-7241 Study Identifier] Observational Study Protocol

		NOVOLIN N INNOLET
		NOVOLIN N PENFILL
		RELION HUMULIN N
		RELION NOVOLIN N INNOLET
Long-Acting Insulin	Insulin Glargine Soln Pen-Injector	Basaglar KwikPen
	Insulin Glargine, Recombinant	LANTUS
		LANTUS SOLOSTAR
	Insulin Detemir	LEVEMIR
		LEVEMIR FLEXPEN
		LEVEMIR FLEXTOUCH
Insulin Glargine, Recombinant	TOUJEO	
Insulin Degludec	TRESIBA	
Pre-Mixed Insulin	Insulin Lispro Protamine/insulin Lispro	HUMALOG MIX 50/50
		HUMALOG MIX 75/25
		HUMALOG MIX 75/25 PEN
	Insulin Human Isophane (nph)/insulin Human Regular	HUMULIN
		HUMULIN 50/50
		HUMULIN 70/30
		HUMULIN 70/30 KWIKPEN
		HUMULIN 70/30 PEN
	Insulin Beef Regular/insulin Pork Isophane (nph)	Iletin NPH I
	Insulin Human Isophane (nph)/insulin Human Regular	NOVOLIN 70/30
		NOVOLIN 70/30 INNOLET
		NOVOLIN 70/30 PENFILL
	Insulin Aspart Protamine/insulin Aspart	NOVOLOG MIX 70/30
		NOVOLOG MIX 70/30 FLEXPEN
Insulin Human Isophane (nph)/insulin Human Regular	RELION HUMULIN 70/30	
	RELION NOVOLIN 70/30	
	RELION NOVOLIN 70/30 INNOLET	
Rapid-Acting Insulin	Insulin Glulisine	APIDRA
		APIDRA SOLOSTAR
	Insulin Lispro, Recombinant	HUMALOG
		HUMALOG KWIKPEN
		HUMALOG PEN
		LISPRO-PFC
	Insulin Aspart, Recombinant	NOVOLOG
		NOVOLOG FLEXPEN
NOVOLOG PENFILL		
Short-Acting Insulin	Insulin Human Regular, Buffered	HUMULIN BR
	Insulin Human Regular	HUMULIN R

[2018-7241 Study Identifier] Observational Study Protocol

		INSULIN HUMAN REGULAR
		NOVOLIN 70/30 PENFILL
		NOVOLIN N PENFILL
		NOVOLIN R
		NOVOLIN R INNOLET
		NOVOLIN R PENFILL
		RELION HUMULIN R
		RELION NOVOLIN R
	Insulin Human Regular, Buffered	VELOSULIN BR
U-500R	Insulin Human Regular	HUMULIN R CONCENTRATED U-500
		HUMULIN R CONCENTRATED U-500 KWIKPEN

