6.4 Other Analyses**6.4.1 Outcomes Analyses**

All the analyses will be performed separately in VHA, linked Truven claims and EMR data, Truven claims database, and the pooled VHA and linked Truven claims and EMR data.

Pooling Multiple Databases

The VHA and linked Truven Claims with EMR databases will be pooled. To remove potential duplicate patient records from multiple data sources, probabilistic matching will be utilized. Potential duplicate patients across the databases will be identified by a STATinMED Research algorithm using age, sex, hospital admission date, hospital discharge date, and primary discharge diagnosis.^{23,24} Identified patients with the same information for the variables listed above will be assumed to be the potential duplicated patient and flagged in the pooled dataset. The rate of duplicate patients is expected to be low based on references and a previous study (<1%).²³ Duplicate patients can be potentially retained in the analytic file if the rate is low. After pooling, we will check if there are any potential duplicates across datasets. If the % will be small (<3%), we will not delete any duplicates because the impact to the final outcomes are considered minimal. If the % is significant (>3%), we will remove the duplicated records from the dataset that has the

[2018-7241 Study Identifier] Observational Study Protocol

larger sample size. Analyses will be conducted on each individual database as well as the pooled dataset.

Research Objective 1: Primary Objective 1Descriptive Analysis

All study variables including demographics, clinical characteristics, and treatment patterns of insulin (i.e., TDD, adherence, prescription fill rate, claim gaps, persistence, and concomitant medication use) will be analyzed descriptively before and after U-500R syringe initiation and U-500R Kwikpen initiation, and before and after U-500R device switch from syringe to Kwikpen.

Numbers and percentages will be provided for dichotomous and polychotomous variables. Means and standard deviations (SDs) will be provided for continuous variables. McNemar's test will be used to determine statistical significance of before and after values for categorical variables, and the paired t-test will be used to assess the statistical significance of before and after values in continuous variables.

Multivariate Analysis

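### In VHA, LCED and pooled data, Primary Objective 1 is restricted to patients with HbA1c tests, one of them after index, although it uses no HbA1c value; MarketScan is exempt

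*Protocol*

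**What the plan says.** Section 5.3.1 lists two HbA1c requirements for each of the three cohorts. The first is at least one "HbA1c measurement within 90-day pre-index or 30-day post-index event". The second, for syringe and Kwikpen initiators, reads "Include patients who had ≥ 1 HbA1c measurement after the 30-day post-index period at any time in the 9-months follow-up period". The device-switcher version asks for at least one "HbA1c measurement after the 30-day post-index period" and writes no 9-month limit in that bullet.

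The Note closing the criteria gives one exemption. Because MarketScan claims hold no laboratory data, "the criteria to have at least 1 HbA1c will be removed from the inclusion criteria while using this database". No objective is exempted.

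Section 5.3.2 then fixes the analysis sets: "After applying the inclusion and exclusion criteria, our analysis will focus on the following cohorts". Table 1 assigns Primary Objective 1 to VHA, to pooled VHA and LCED, and to MarketScan claims. Section 6.4.1 adds LCED alone: "All the analyses will be performed separately in VHA, linked Truven claims and EMR data, Truven claims database", and also in the pool.

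**The concern.** The Primary Objective 1 outcomes are pharmacy-claims measures in Table 3, and the adherence model in Section 6.4.1 has no HbA1c covariate. The MarketScan waiver itself shows that the objective can be answered without a laboratory value.

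The second criterion is the more serious one, because it conditions on something that happens after index. A patient who stops U-500R and then has little contact with care may have no HbA1c after day 30. That patient leaves the cohort before being counted as non-persistent.

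Two things are at stake. First, post-index persistence in VHA, LCED and the pool may describe a selected group. Second, Section 5.1 presents the separate and pooled analyses as together giving a fuller real-world picture. With unequal entry rules, a difference between VHA and MarketScan on the same objective mixes population with eligibility.

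**Working it through.** **Which analyses use an HbA1c value**

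- Primary Objective 1, descriptive and adherence model: no.
- Primary Objective 2, with its mediation analysis: yes, as the outcome.
- Secondary Objective 2a, descriptive hypoglycemia counts: no.
- Secondary Objective 2a, zero-inflated negative binomial model: yes. HbA1c before and after index is a time-varying covariate.
- Secondary Objective 2b: yes. It is defined on a subset with HbA1c available.
- Primary Objective 3: no, but Table 1 runs it in MarketScan only, where the criteria are waived.

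The criteria therefore reach further than needed in Primary Objective 1 (VHA, LCED, pooled) and in the descriptive part of 2a.

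**Which outcomes could be affected**

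Table 3 defines persistence on the index medication in every cohort, so stopping U-500R counts directly. Days covered after index counts any insulin for initiators but only U-500R Kwikpen for device switchers. Stopping U-500R thus lowers days covered directly only in switchers.

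**What Table 4 can show**

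The protocol gives no power calculation and no windowed testing rate. Its only related figures are raw VHA counts with at least two HbA1c values:

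- Kwikpen: 4,066/4,120 = 98.7%; 54 patients (1.3%) without.
- Vial: 5,718/5,863 = 97.5%; 145 patients (2.5%) without.

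Assume true persistence of 60%. If every untested patient were non-persistent, observed persistence would be 0.60/0.9869 = 60.8% and 0.60/0.9753 = 61.5%. If every one were persistent, it would be (0.60 − 0.0131)/0.9869 = 59.5% and (0.60 − 0.0247)/0.9753 = 59.0%.

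These are not limits on the effect of the eligibility rule. Table 4 counts any two values under a five-year heading, states no index-related window, precedes the other criteria and has no LCED row.

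**Illustration for the windowed criteria**

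Let P be true persistence, and t1 and t0 the probabilities that persistent and non-persistent patients meet both HbA1c criteria. All three are assumptions. Then

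observed persistence = P·t1 / [P·t1 + (1 − P)·t0],

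and the shift is P(1 − P)(t1 − t0) / [P·t1 + (1 − P)·t0]. Its sign is the sign of t1 − t0. With P = 60%:

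| t1 / t0 | Share retained | Observed persistence | Shift (points) |
|---|---|---|---|
| 95% / 95% | 95% | 60.0% | 0 |
| 95% / 90% | 93% | 61.3% | +1.3 |
| 95% / 85% | 91% | 62.6% | +2.6 |
| 90% / 70% | 82% | 65.9% | +5.9 |
| 85% / 55% | 73% | 69.9% | +9.9 |

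For example, 90%/70% gives 0.54/(0.54 + 0.28) = 0.659. Over P = 50% to 70% with the same rates, the shift runs from 0 to +10.7 points. The maximum is at P = 50% and 85%/55%: 0.425/0.70 = 0.607, with 30% of patients lost.

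**The case against.** The strongest defence has four parts.

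- **A common cohort is coherent.** The mediation analysis needs adherence and HbA1c in the same patients. This stands as a reason to report Primary Objective 1 in the tested subset, but not as a reason to report it only there.
- **Continuous enrollment for 9 months after index already conditions on follow-up in every database.** That is so, but it requires coverage, not contact with care. The HbA1c rule is a further filter, in some databases only.
- **The MarketScan difference is declared, no formal cross-database test is planned, and MarketScan already supplies an estimate of Primary Objective 1 without this filter.** All true. It limits the damage, but the VHA and pooled estimates remain conditional on testing.
- **The direction is not shown.** A patient who stops U-500R for another insulin may stay in care and be tested. This stands: nothing in the protocol links stopping to missing tests.

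A reader might also infer more than the protocol supports. It is tempting to say that all objectives are affected, but Primary Objective 3 is not, and Primary Objective 2, the 2a model and 2b need HbA1c. It is tempting to free the whole hypoglycemia analysis, but its regression model uses HbA1c as a covariate. Nor should 2a be extended to MarketScan: Table 1 does not place it there, and the event definition includes a blood glucose cutoff that a database without laboratory data cannot apply.

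**Conclusion.** The point holds for Primary Objective 1 in VHA, LCED and pooled data, and for the descriptive part of Secondary Objective 2a. Entry to these analyses depends on a test in the outcome period that they do not need, and the same primary objective has a different entry rule in MarketScan.

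Persistence may be overstated, and so may U-500R days covered in device switchers. For initiators' days covered the case is weaker, because any insulin counts. Reading this as a demonstrated upward bias would go too far. The 0 to about 11 points rests wholly on assumed persistence and testing rates, in which non-persistent patients are tested no more often than persistent ones; if they were tested more often, the sign would reverse. Table 4 proves neither a large loss nor a negligible one.

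**What to change.** State in the Note to Section 5.3.1 that the HbA1c criteria apply only to analyses that use HbA1c: Primary Objective 2 with its mediation analysis, the Secondary Objective 2a regression model, and Secondary Objective 2b.

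Run Primary Objective 1 without them in all its databases. Run the descriptive 2a analysis without them in its Table 1 databases only (VHA, LCED, pooled). Report Primary Objective 1 in the HbA1c-tested subset as a sensitivity analysis, so that it lines up with the mediation population and shows how much the criteria change the result.

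No new data are needed, and the Primary Objective 1 sample can only grow. The cost is a short change to the Note and two denominators per affected database, both shown in the attrition table.
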